#### **43. Recruitment potential (number of subjects to be recruited)**

25 subjects for a diet in 3 meal times.

25 subjects for a diet in 6 meal times.

#### **44. If it is multicentre, include the global number and the local number of the sample**

N/A

#### **45. Procedures for reporting deviations from the original statistical plan**

Amendments will be sent to the research ethics committee and the institute's research committee if it is intended to report a deviation from the original statistical plan.

#### **46. Possible discomfort resulting from the study**

Sensor Placement

Change of eating habits

#### **47. Potential risks**

hypoglycemia
48. Early risk detection methods
N/A
49. Security measures for timely diagnosis and risk prevention
N/A
50. Procedures to follow to resolve risks in case they arise
N/A
51. Expected direct benefits

 
-Weight reduction.
 
-The study will establish whether the VG is different within a group of individuals with a 3-meal meal plan & one with 6 mealtimes.
 
-Improvement in glycemic control reflected by fasting glucose and glycosylated hemoglobin.
 

52. Expected indirect benefits

 
-Decrease of triglycerides
 
-Decrease in Cholesterol
 
- Decrease in systolic blood pressure figures
 
-Improved recommendations for a meal plan for diabetic patients.
 
-Better control of Hunger-Satiety.
 

53. General weighting of risks against benefits of the proposed study
According to the previously published evidence, it is estimated that the benefits outweigh the risks
54. Specify costs (direct / indirect, monetary, in time of participation, visits / transfers) that the research generates for the subjects of the study
The study including consultations, laboratories and medical treatment will have no cost to the patient, the patient will only have to pay the cost of transportation to attend their visits.
55. Specify whether the consultations, laboratory / cabinet exams and medical / surgical treatments generated during the study will or will not be covered by the patient / research subject
The study including consultations, laboratories and medical treatment will have no cost to the patient, the patient will only have to pay the cost of transportation to attend their visits.
56. Report who will cover the costs associated with the investigation
Medtronic glucose sensors
57. If applicable, specify the incentives that will be offered (an incentive is understood as an offer or influence that compels to carry out an action without implying a significant deviation from our general life plan; v. Gr.: give a book for having participated)
Note: A compensation / incentive out of proportion is considered a coercive attitude
N/A
58. Bibliographic citations.

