#### **35. Criterios para el retiro prematuro del estudio**

- Manifest desire of the patient to withdraw from the protocol.
- What is not complying with the meal times that correspond to a patient's personal problem.
- Frequent hypoglycemias, genital infections, urinary tract infections, euglycemic ketoacidosis, anasopharyngitis and orthostatic hypotension that require hospitalization for the assessment and control of the patient's clinical condition.

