#### **36. Procedures for the withdrawal of a patient from the study**

- Removal of data obtained through patient participation
- Valuation by medical specialists of the department.
- Assessment by department nutritionist.
- A conventional food plan is given.

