#### **38. Selection criteria**

- a) Inclusion criteria (It must include the definition of the age groups, sex and the severity of the condition that will be allowed in the study)
  - a) Individuals with type 2 diabetes
  - b) Less than 10 years of evolution

c) Age between 40 and 70 years
 
d) Both genders.
 
e) With oral treatment scheme (oral hypoglycemic agents).
 
f) With HbA1c <9%
 
g) With BMI <math>\geq 25</math> to <math><40</math> kg / m^2

b) Exclusion criteria

a) Individuals with another type of diabetes.
 
b) Use of insulin.
 
c) Evolution time of more than 10 years.
 
d) Hospitalization in the last 3 months
 
e) Disease with poor short-term prognosis (for example: cancer)
 
f) Acute infection or febrile syndrome
 
g) Chronic disease other than those to be evaluated, for example: HIV, rheumatic diseases, liver cirrosis
 
h) Pregnancy
 
i) Who do not wish to participate in the study

c) Elimination criteria

a) Men or women who do not wish to continue in the study
 
b) Individuals who do not tolerate the placement of the MCGI
 
c) Individuals who are not attached to the meal plan.
 
d) Individuals who do not respect the corresponding meal times during the study.

39. Outcome and variables

a) Main variables / outcomes to be measured
 
BMI (kg / m^2)
 
a) Weight
 
Glycemic variability, defined with the following indices:
 
a) MAGE (mean amplitude of glycemic excursions)
 
b) MODD (mean of daily differences)
 
c) CONGA-n
 
b) Secondary outcomes to be measured:
 
a) Fasting glucose
 
b) Triglycerides
 
c) Total Cholesterol
 
d) HbA1c
 
e) Oxidative stress
 
f) FGF21
 
g) Systolic and diastolic BP
 
h) Hunger-Satiety Scale
 
a) Frequency of measurements:

Three measurements will be made in a 12-week period with a 6-week interval between each measurement, however the sensor placed in visit 2 will be left for 7 days during which glucose measurements in the interstitial fluid will be obtained every 5 minutes.

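### Hypoglycaemia is the named risk, yet section 50 gives no response to it, and section 36, read literally, removes the safety records of patients withdrawn for it

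*Protocol*

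**What the plan says.** Protocol section 47 lists one potential risk, hypoglycaemia. The next three headings ask how it will be handled: section 48, "Early risk detection methods"; section 49, "Security measures for timely diagnosis and risk prevention"; section 50, "Procedures to follow to resolve risks in case they arise". Each is answered N/A.

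Other sections bear on the same risk:

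- Section 16 asks for a once-daily home glucose check.
- Section 29 lists capillary glycaemia and adverse-event documentation. The layout leaves open whether these are one form or two.
- Section 20 (rescue therapy) lists SGLT2 inhibitors, DPP4 inhibitors, insulin and GLP1.
- Section 35 gives as a withdrawal ground "Frequent hypoglycemias, genital infections, urinary tract infections, euglycemic ketoacidosis, anasopharyngitis and orthostatic hypotension that require hospitalization". The closing words on hospitalization may qualify the whole list or only its last items.
- Section 36 gives the steps at withdrawal. The first is "Removal of data obtained through patient participation"; the second is "Valuation by medical specialists of the department".
- Section 37 allows the study to be suspended for undesirable side effects and sets no threshold.
- Section 38c(d) eliminates "Individuals who do not respect the corresponding meal times during the study".

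**The concern.** N/A cannot be the right answer to how a risk will be resolved when the same form has just named that risk and section 35 treats its frequent occurrence as foreseeable. Two consequences deserve attention.

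The first is the safety record. If withdrawal for hypoglycaemia triggers removal of the patient's data, the patients most informative about the one named risk drop out of what is reported. The record would then err towards reassurance.

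The second is specific to this trial. Meal frequency is the intervention, and the usual remedy for a low is to eat at once, which may be between planned meals. A rule that eliminates patients for not respecting meal times, with no exemption, could be read to penalise that remedy.

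**Working it through.** The point is textual. No figure in the plan depends on it, so the check sets the sections side by side.

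1. **Detection and prevention (48, 49).** Section 48 is N/A, but section 16 has a home glucose check and section 29 has capillary and adverse-event documentation. The tools exist, so most of this defect is a missing cross-reference. What none of them carries is a threshold, a review rule or an action. The 7-day sensor is not counted as early detection: sections 28 and 39 describe it as a measurement of glucose and its variability, and nothing says that it is read in real time.

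2. **Response (50).** The candidates elsewhere are sections 20, 35, 36 and 37. Section 20 lists only glucose-lowering drugs, which do not treat a low. Sections 35 and 37 offer withdrawal of the patient or suspension of the study. Section 36 adds specialist assessment, but only at withdrawal. None says what is done about a low in a patient who stays in the trial. The text available has 0 glucose thresholds and 0 treatment steps.

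3. **Records (35 with 36).** Frequent hypoglycaemia leads to withdrawal, and withdrawal leads to removal of data. No exemption for adverse events or glucose records is stated. Lows in patients who are not withdrawn are unaffected.

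4. **Size, under assumed counts only.** The protocol gives no hypoglycaemia rate. With 25 patients per arm and *k* withdrawn for hypoglycaemia, the true proportion is *k*/25:
   - *k* = 1: 1/25 = 4%
   - *k* = 2: 2/25 = 8%
   - *k* = 3: 3/25 = 12%
   - *k* = 5: 5/25 = 20%

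   Under literal removal these patients contribute 0 events in every case.

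5. **Treating a low (38c(d), 35).** Criterion 38c(d) has no exemption for food taken to treat a low. Section 35 also lists "not complying with the meal times", but goes on to tie this to a personal problem of the patient. The translation is unclear, and the qualifier probably narrows it. The wording therefore permits a penalising reading without requiring one.

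**The case against.** The strongest reply is that the protocol is not blind to hypoglycaemia. It has home checks, adverse-event documentation, specialist assessment at withdrawal and a suspension criterion, and section 25 sends problems to departmental research sessions. The expected rate is probably low, because section 21 names only metformin and section 22 prohibits insulin. Section 36 does not mention adverse-event records and may mean only exclusion from the analysis file. Much of this stands. The team would probably know of a case, so the concern is limited to what is reported and to the missing response step. If section 36 means the analysis file only, it should say so.

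Several stronger readings are tempting, and the documents do not support them:

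- **That a low home reading could wait 42 days for review.** The last two visits are 6 weeks apart (6 × 7 = 42 days). But section 16 gives the home-glucose instruction at visit 1, in the same sentence as a one-week food diary, and does not say how long testing continues. The figure holds only if testing runs through follow-up.
- **That patients receive no instructions.** Consent pages were removed from the review copy and may contain them.
- **That treating a low is itself an elimination event.** Criterion 38c(d) reads naturally as non-adherence. An exemption is a worthwhile clarification, not the repair of a proven contradiction.
- **That withdrawal is the only stated consequence.** Section 37 also provides for suspension of the study.

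None of these limits makes N/A correct in section 50 or supplies the exemption missing from section 36.

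**Conclusion.** The concern holds in a limited form and should be corrected. Three parts stand. Section 50 gives no response to the risk named in section 47, and the text available supplies none elsewhere. Sections 48 and 49 deny measures that the protocol partly has. Section 36, if read literally, takes patients withdrawn for hypoglycaemia out of the reported safety record. The lack of an exemption in 38c(d) is a smaller point, but it matters more than usual where meal timing is the treatment.

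The number of patients affected cannot be estimated from the documents and is probably small. In a trial of 50, however, even one lost case is 4% of an arm. The records part rests on the literal reading of section 36. The finding makes no claim about the weight or glycaemic variability comparisons.

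**What to change.** - **Section 36:** state that adverse events and glucose records up to withdrawal are kept and reported in the assigned group. If the removal step is meant only for the analysis file, say so.
- **Sections 38c(d) and 35:** state that food taken to treat a low is not a breach of meal times.
- **Section 48:** replace N/A with the existing home glucose log and adverse-event form, and state how long home testing runs.
- **Sections 49 and 50:** set a low-glucose threshold. The choice is the sponsor's; 70 mg/dL is an example, not a figure from the protocol. For a value below it, or a symptomatic episode, specify oral carbohydrate, a retest, a prompt report, and study-physician review of the meal plan and drugs. Match this to whatever the consent material already tells patients.

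The cost is amendment wording in sections 35, 36, 38c and 48 to 50, with a patient instruction sheet if none exists. No visits or laboratory tests are added.
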